### **5.3.7 *ADHD Treatment after Study Completion or Early Withdrawal***

At the end of the study or at early withdrawal the investigator (in consultation with the subject/parent/caregiver) may resume the subject's usual ADHD treatment. In the event that the subject experiences intolerable side effects or the subject's ADHD symptoms worsen while in the study, the subject may be discontinued from the study and their usual ADHD treatment may be resumed at the discretion of the investigator (in consultation with the subject/parent/caregiver). The investigator may continue to provide up to 3 months care for behavior and medication management.

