#### 6.17 Adverse events

Per the International Conference of Harmonization (ICH), an adverse event is any untoward medical occurrence in a subject administered a pharmaceutical product that does not necessarily have a causal relationship with the treatment. An AE can therefore be any unfavorable and unintended sign, symptom, or disease temporally associated with the use of a medicinal product, whether or not considered related to the medicinal product. Pre-existing events, which increase in frequency or severity or change in nature during or as a consequence of use of a drug in

Amendment 4: Version 5.0 May-08-2013

Amendment 3: Version 4.0 December-11-2012

Amendment 2: Version 3.0 October-31-2012

Amendment 1: Version 2.0 August-02-2012

Final Protocol May-25-2012

clinical trials, will also be considered an AE. Adverse events may also include pre- or post-treatment complications that occur as a result of protocol-mandated procedures (e.g., invasive procedures such as biopsies).

Any medical condition or clinically significant laboratory abnormality with an onset date before the date of signing of Informed Consent is considered to be pre-existing, and should be documented as Medical History. Any new medical condition or clinically significant laboratory abnormality or an exacerbation of a pre existing condition with an onset date after signing of Informed Consent should be recorded as an AE.

Adverse events will be collected throughout the study beginning from the time the subject signs the consent form and up to 30 days following last patch removal. For all AEs the Investigator must pursue and obtain information adequate both to determine the outcome of the AE and to assess whether it meets the criteria for classification as a serious AE requiring immediate notification. Ongoing AEs, at the End of Study or Early Termination, will be followed until the event resolves or stabilizes at a level acceptable to the Investigator or up to 30 days after last patch removal, whichever occurs first. Follow-up beyond 30 days should be discussed with the medical monitor.

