Age will be calculated as (date of informed consent – date of birth + 1) / 365.25.

Baseline

Baseline is defined as data collected at Visit 0 (Day 0). If data was not collected at Visit 0, the last data available prior to Visit 0 will be used as the baseline data. However during the double

blind crossover phase change from baseline analyses will be performed taking the pre-dose data at the same classroom visit to be the baseline.

Body Mass Index

Body Mass Index (BMI) will be calculated as weight in kg / (screening height in m)².

Prior and Concomitant Medications

Prior medications are defined as those taken prior to the date of first dose of study medication. Concomitant medications are defined as those on or after the date of first dose of study medication through and including the day of the safety follow-up visit. Medications with a missing or incomplete start date will be assumed to be concomitant.

Concomitant medications will be assigned to either the Dose-Optimization Period or the double-blind Treatment Period of the study according to the start date, and will be summarized separately. Concomitant medications for which a missing or incomplete start date makes it impossible to determine which period of the study they started in will be counted as starting in the Dose-Optimization Period.

Treatment-emergent adverse event

A treatment-emergent adverse event (TEAE) is one which first occurs or worsens in severity after the first patch application and not later than 30 days following last patch removal. Adverse events are collected through the last study visit. Those AEs with a start date equal to the date of first patch application will be considered as TEAEs.

Adverse events for which a missing or incomplete start date makes it impossible to determine whether or not they were treatment-emergent will be counted as being treatment-emergent.

Adverse events will be assigned to either the Dose-Optimization Period or the double-blind Treatment Period of the study according to the start date, and will be summarized separately. Adverse events for which a missing or incomplete start date makes it impossible to determine which period of the study it started in will be counted as starting in the Dose-Optimization Period

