7.7.1 Adverse Events

Treatment-emergent adverse events will be assigned to either the open-label Dose-Optimization Period or the double-blind Treatment Period. TEAEs occurring in the safety follow up after the double blind Treatment Period will be reported under the double blind Treatment Period for the last treatment they received. TEAEs for which a missing or incomplete start and/or stop date makes it impossible to determine which period of the study they started in will be counted as starting in the Dose-Optimization Period. The subject's dose of study drug at the onset of the event will be determined for all TEAEs. If a missing or incomplete start date makes it impossible to determine the dose at onset, then the dose at onset will be set to the lowest dose in the study (i.e., 5 mg/ 4.76 cm²). Adverse events that start before the first patch application will be summarized separately. For summaries, TEAEs with missing severity are assumed to be severe, and TEAEs with missing relationship to study drug are assumed to be related.

Summary statistics for TEAEs will be presented separately for the SP population on all subjects combined during the Dose-Optimization Period and by treatment arm during the double-blind Treatment Period. All summaries of adverse events will consist of the number of events and the numbers and percentages of subjects who had the events being summarized.

All TEAEs will be classified by SOC and PT using the latest version of MedDRA dictionary. All TEAEs that occur after first patch application up to 30 days following last patch application will be summarized. Subjects may have more than one TEAE per SOC or PT. Unless otherwise specified, at each level of subject summarization in reporting the incidence of the AE, a subject will be counted once if the subject reported one or more events.

The following summaries will be presented separately for the Dose-Optimization Period and the double-blind Treatment Period by the dose being taken at the onset of the events and by MedDRA SOC, and preferred term:

- Overall summary of TEAEs
- TEAEs
- Treatment-related TEAEs
- TEAEs leading to premature discontinuation of study drug
- TEAEs by intensity.

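### Follow-up adverse events are credited to the last study treatment, with no exception or flag when usual ADHD medication has been restarted

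*SAP*

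**What the plan says.** SAP section 5 uses two period categories: "Adverse events will be assigned to either the Dose-Optimization Period or the double-blind Treatment Period of the study according to the start date". An event is treatment-emergent if it first occurs or worsens after the first patch and "not later than 30 days following last patch removal". SAP 7.7.1 repeats the window, counting from application rather than removal ("All TEAEs that occur after first patch application up to 30 days following last patch application will be summarized"), a difference of hours that does not matter here.

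For follow-up events the SAP is explicit: they "will be reported under the double blind Treatment Period for the last treatment they received". The summaries are also to be presented "by the dose being taken at the onset of the events". Only events that start before the first patch are summarized separately.

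Protocol 5.3.7 says that at the end of the study or at early withdrawal the investigator, in consultation with the family, "may resume the subject's usual ADHD treatment". It adds: "The investigator may continue to provide up to 3 months care for behavior and medication management". The protocol synopsis makes Visit 7 (Day 49) the End of Study visit. Protocol 5.3.8 schedules one later contact, a telephone call 7 to 10 days after the last dose, which records adverse events and concomitant therapy.

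**The concern.** From Day 50 a completer wears no study patch and may already be back on another ADHD drug. An event that begins then still enters the double-blind table under d-ATS or placebo, whichever came second. For a child who finished on placebo, insomnia from a restarted stimulant becomes a placebo event. For a child who finished on d-ATS, the same event becomes a d-ATS event. Early withdrawal can have the same effect: protocol 5.3.7 allows a child whose symptoms worsen to be discontinued and returned to usual treatment. If that happens on placebo, later events are placebo events.

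Safety of d-ATS is a primary objective. Protocol 6.19 expects its adverse-event profile to resemble that of oral d/l-amphetamine, so a restarted amphetamine could produce the same events that the table is meant to compare. With 1:1 sequences, about half of completers' post-restart events would fall in each column. Because the placebo rate is expected to be the lower one, it is raised proportionately more, and d-ATS looks closer to placebo.

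**Working it through.** The plan states no figure for this point, so there is none to reproduce. The check has two parts.

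**1. How much of each column's time is off treatment**

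Inputs: double-blind dosing on Days 36 to 49 (protocol 5.1), so 42 − 36 + 1 = 7 days and 49 − 43 + 1 = 7 days per treatment; 74 expected completers (SAP 3.1); 1:1 sequences (SAP 3.2), so 37 children finish on each treatment; follow-up contact 7 to 10 days after the last dose (protocol 5.3.8).

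- On-treatment child-days per column: 74 × 7 = 518.
- Follow-up child-days added to each column: 37 × 7 = 259 for a call at 7 days; 37 × 10 = 370 for a call at 10 days.
- Off-treatment share: 259 / (518 + 259) = 259/777 = 33%; 370 / (518 + 370) = 370/888 = 42%.

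For an individual child, the second treatment is credited with 14 or 17 days against 7 for the first, so 7/14 = 50% or 10/17 = 59% of its window is off treatment. These are shares of time, not of events.

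**2. What a restart could do to the rates (assumptions only)**

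Let p be the true on-treatment rate of a given event. Let s be the chance that a child restarts ADHD medication and then has that event before the call. The documents supply neither. With half the children finishing on each treatment, and assuming independence:

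reported rate = p + 0.5 × s × (1 − p)

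Take p = 20% on d-ATS and 5% on placebo.

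| s | d-ATS | Placebo | Ratio | Difference (points) | Placebo children of 74 |
|---|---|---|---|---|---|
| 0 | 20.0% | 5.0% | 4.0 | 15.0 | 3.7 |
| 5% | 22.0% | 7.4% | 3.0 | 14.6 | 5.5 |
| 10% | 24.0% | 9.8% | 2.5 | 14.3 | 7.2 |
| 20% | 28.0% | 14.5% | 1.9 | 13.5 | 10.7 |

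The difference is multiplied by (1 − s/2), so it barely moves; the placebo rate and the ratio move more. Nothing in the documents supports a value as high as 20%; it only marks the end of the range.

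For scale, 14.8 against 3.7 children of 74, with the columns treated as independent, gives a standard error for the log ratio of √(1/14.8 − 1/74 + 1/3.7 − 1/74) = 0.56. The rough 95% interval around 4.0 is 1.3 to 11.9, and every ratio in the table lies inside it.

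**The case against.** The strongest reply is that this is a stated convention, not an omission: the SAP says where follow-up events go. That stands, and it also supplies a treatment label for follow-up events even though no study dose is being taken at their onset. What it lacks is an exception or flag for a new active drug.

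A second reply is that protocol 7.4.3 bars other stimulants for the whole study, which the protocol puts at about 56 days. The tension is real. But 5.3.7 expressly permits resumption at the end of the study, and Visit 7 is named as that visit, so resuming from Day 49 is a fair reading.

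A third is that the effect may be small. Resumption is optional, and washout applies only to children already on medication. Usual treatment need not be an amphetamine: 7.4.3 also lists methylphenidate and atomoxetine. All of this stands and limits the weight of the point.

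Existing safeguards help in part. Treatment-related events have their own summary, and a probable rating requires that other therapy not reasonably explain the event. But a possible rating admits events that other therapy may have produced, missing relatedness is counted as related, and the investigator rates without knowing which treatment came last. Relatedness does not alter the table of all treatment-emergent events. Dated listings allow a reader to find affected events by hand but leave the table as it is.

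Three stronger readings do not hold:

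- A reader might run the time calculation to the 30-day limit, since protocol 6.17 collects events "up to 30 days following last patch removal". SAP section 5, however, says that collection ends with the last study visit, and the only scheduled contact after treatment is the call. The 7-to-10-day range is what scheduled ascertainment supports.
- A reader might take the double-blind table as the main safety evidence. Neither document says so. A completer has about 35 d-ATS days in dose optimization against 7 in the double-blind period, and the dose-optimization table is separate and, for randomized children, untouched by this rule.
- A reader might infer that concomitant medications are misattributed by arm too. SAP 7.4.2 presents them by period, not by treatment, so no such error follows.

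**Conclusion.** The point holds as a low-cost improvement to the safety tables. The stated rule can place events caused by a restarted drug in the d-ATS or placebo column, and the planned tables give no way to tell them apart. For completers, 33% to 42% of each column's time is after the last patch, given 7 days per treatment, equal sequences and a call at 7 to 10 days. The effect on event rates is unknown because no restart rate is given. Under the illustrative assumptions it is modest: it shows in the placebo rate and the ratio, while the absolute difference stays within 1.5 points of 15 even at the top of the range. No safety inference is planned, and the SKAMP analysis, the Completers population, power and alpha are unaffected.

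**What to change.** In SAP sections 5 and 7.7.1, keep the current table by last treatment received. Beside it, present the double-blind events with a separate follow-up column for those starting more than a short, stated interval after removal of the child's own last patch. Split that column by whether ADHD medication was restarted before onset (yes, no, unknown), using the medication dates recorded through the follow-up call. Keying the rule to each child's own last patch covers early withdrawals.

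The sponsor should set the interval from its pharmacokinetic data so that delayed and withdrawal events stay with d-ATS. An arbitrary next-day cutoff could remove them.

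Using the same follow-up category for concomitant medications in SAP 5 and 7.4.2 would be tidy but is optional.

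The cost is a couple of SAP sentences, one extra column and minor programming, with no new data needed for events up to the call. The downsides are that some late d-ATS events would appear beside the d-ATS column rather than in it, and that restart status may be unknown for any event reported after the call, because concomitant medication is defined only through that contact.

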6. ANALYSIS POPULATIONS

6.1 FULL ANALYSIS SET

The full analysis set (FAS) includes all consented and randomized subjects who have taken at least one dose of study medication. The FAS population will be used as the primary population for analysis of efficacy endpoints.

6.2 COMPLETERS

The completers population includes all consented and randomized subjects who

- received full prescribed dose of the double-blind study medication at both test laboratory classroom sessions
- completed the full classroom tests on both test classroom sessions
- did not miss more than four consecutive days of therapy during the double blind treatment period

- did not use prohibited concomitant medications during the double blind treatment period

The Completers population will be used for supportive analyses of efficacy endpoints.

6.3 SAFETY

The safety (SP) population includes all subjects who have taken at least one dose of the study medication and have at least one post dose safety measurement (including dermal assessments). In the unlikely event that errors may have occurred in treatment arm assignments, analyses using the Safety population will be based on treatment actually received. The SP population will be used for the analysis of dermal evaluations and safety endpoints.

7. STATISTICAL METHODS

Summaries will be presented for the SP population for all subjects combined during the Dose-Optimization Period of the study. During the double-blind Treatment Period of the study, summaries will be presented for the FAS, Completers, and SP populations by treatment (i.e., d-ATS and placebo, with all d-ATS dose levels combined), and some tables by treatment and treatment sequence. Subjects are intended to receive both treatments during the double-blind cross-over period of the study, so summaries for Visits 6 and 7 will be combined, with subjects contributing data to both treatment columns for the combined time point. As a result, the numbers of subjects in each treatment arm in the header of these summaries will reflect the total number of subjects receiving the treatment, and the number of subjects contributing data for each visit will be presented in the body of the table.

Early termination visits will be mapped to the next scheduled visit for inclusion in summary tables, where appropriate. For example, a subject who terminates after Visit 3 (e.g., has assessments at Visits 1 - 3 and early termination assessments) would have assessments from early termination mapped to the next scheduled visit for each assessment. Different assessments may be mapped to different visits; in this example, most assessments would be mapped to Visit 4, ECG would be mapped to Visit 5 as no ECG assessments are scheduled to be performed at Visit 4. This mapping is considered part of the observed values, and will be conducted before any summaries or analyses are performed on observed values. Similarly, it will be conducted before any scoring algorithm is applied. Listings will present early termination data as the mapped visit, as well as under 'ET' Visit as well.

Unless otherwise noted, categorical variables will be summarized using counts and percentages. Percentages will be rounded to one decimal place, except 0% and 100% will be displayed without any decimal places. Continuous variables will be summarized using the number of observations (n), mean, standard deviation (SD), median, minimum, and maximum. All analyses will use SAS® version 9.1 or higher.

All raw data will be presented to the original number of decimal places. The means and medians will be presented to 1 more decimal place than the raw data. The standard deviations will be presented to 2 more decimal places than the raw data.

To preserve the Type I error rate in analyzing the secondary endpoints of onset and duration of efficacy, a closed test procedure will be used. The closed test principle states that the trial-wise error rate can be controlled by the ordered testing of each hypothesis in the closed family using a suitable α level significance. A condition of the Closed Test procedure is that the order of testing

of the endpoints in a family matters. Thus hypotheses in a family must be ordered and the testing of each subsequent hypothesis in the order can only proceed if the testing of the prior hypothesis achieves a significant p-value with Type I error rate of predetermined α level, which will be set at $\alpha= 0.05$ for this study. Testing of the hypotheses in the family proceeds until a hypothesis fails to achieve a significant p-value. If/when a hypothesis in the family fails to achieve significance, then significant p-values cannot be claimed for all subsequent hypotheses in that family, i.e., once one hypothesis fails to achieve significance, testing should cease.

If the primary efficacy endpoint, difference between d-ATS and placebo in mean SKAMP total score for the double-blind phase, is statistically significant (i.e., $p<0.05$), the secondary variables of onset and duration of efficacy will be tested using a closed testing procedure. The closed testing procedure starts from the time-point of 1 hour post-morning dose, then 2, 3, 4.5, 6, 7, 9, 10 and 12 hours post-dose. At each timepoint the order of testing will be onset of efficacy followed by duration of efficacy, before moving to the next timepoint. Duration of efficacy will not be considered until onset of efficacy has been determined.

All data collected will be presented in data listings, and the listings will be sorted by investigator/site, subject, and time point.

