**Double-Blind Treatment Period [Day 36 to Day 49; Visit 6 (Day 42) and Visit 7 (Day 49)]:**

Subjects who have reached an optimal dose will be randomized at Visit 5 to receive double-blind treatment. Administration of study medication will begin on Day 36 and continue up to Day 49 (end of Week 7). During Week 6 subjects will receive study patches in accordance with the randomization schedule and during Week 7 subjects will cross-over to receive the other study treatment per the randomization schedule. Subjects/parents/caregivers will be instructed to apply study patches to the hip once daily in the morning at approximately 8:00 am. Patches will be removed after 9 hours. Each day a new patch will be applied to the opposite hip. Subjects will be instructed to continue completing the daily dosing diary and the daily dermal diary. Subjects will return to the clinic for evaluations and analog classroom sessions in the laboratory classroom setting on Visit 6 (Day 42) and Visit 7 (Day 49). Site personnel will contact subjects by telephone on Day 39 and Day 46. All end of study procedures will be completed for subjects who are early discontinuations from the study.

**Follow-Up:** A safety follow-up by telephone 7- 10 days (Visit 8, Day 56 + 3 days) after last dose of study drug.

**Sample Size:** Sufficient number of subjects with ADHD will be screened to randomize approximately 90 subjects. Assuming a 20% dropout rate, it is expected that 74 subjects will complete the study. The Full Analysis Set population (FAS) will be used as the primary population for analysis of efficacy endpoints and is defined as subjects who have taken at least one dose of study medication.

Amendment 4: Version 5.0 May-08-2013

Amendment 3: Version 4.0 December-11-2012

Amendment 2: Version 3.0 October-31-2012

Amendment 1: Version 2.0 August-02-2012

Final Protocol May-25-2012

**Study Duration:** The duration of the study will be approximately 56 days for each individual subject (not including screening and washout).

**Study Population:** The study population will consist of children and adolescents 6 to 17 of age, who have been diagnosed with ADHD.

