### **5.3.6 *Early Termination***

If the subject is discontinued early (prior to Day 49), the following procedures will be performed:

1. Record any AEs or concomitant therapy since previous visit.
2. Perform drug accountability and collect all used and unused patches.
3. Obtain vital signs (sitting BP, HR, RR, oral body temperature).
4. Obtain weight.
5. Collect blood and urine for clinical laboratory assessments
  - Complete Blood Count (including differential and platelet count)
  - Blood Chemistry
  - Urinalysis
6. Perform a 12-lead electrocardiogram (ECG) prior to discharge.
7. Perform complete physical examination
8. Perform urine pregnancy testing on all female subjects of child-bearing potential.

Amendment 4: Version 5.0 May-08-2013

Amendment 3: Version 4.0 December-11-2012

Amendment 2: Version 3.0 October-31-2012

Amendment 1: Version 2.0 August-02-2012

Final Protocol May-25-2012

9. Obtain ADHD-RS-IV score.
10. Perform CGI-I.
11. Administration of the C-SSRS (Children's Since Last Visit version) by a trained staff member.
12. Dismiss from clinic.
13. Contact IVRS/IWRS to early discontinue the subject in the system.

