7.1.3.3 ADHD-RS-IV

Continuous summary statistics will be presented for the ADHD-RS-IV Total, Inattention, and Hyperactivity-Impulsivity scores at each visit from baseline through Visit 7 and for the change from baseline to each subsequent visit for the FAS. The ADHD-RS-IV Total and subscale scores will also be plotted by visit for the FAS.

The ADHD-RS-IV Total and subscale scores at Visits 6 and 7 will be analyzed in a similar way to the primary efficacy analysis, with the exclusion of timepoint from the model. Raw means, LS means, differences in LS means, and 95% CI for the difference between treatment groups, p-values, and model results will be presented for each variable.

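### Mapping early-termination data to the next scheduled visit can, in the crossover, store secondary efficacy and safety values under a treatment the child never wore

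*SAP*

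**What the plan says.** SAP section 7 (Statistical Methods) sets the rule: "Early termination visits will be mapped to the next scheduled visit for inclusion in summary tables, where appropriate". It works assessment by assessment ("Different assessments may be mapped to different visits"), and the result is treated as data: "This mapping is considered part of the observed values, and will be conducted before any summaries or analyses are performed on observed values". The qualifier that closes the first sentence is given no criterion. The only worked example is a child who stops after Visit 3, in the open-label phase, where the next visit carries no randomised treatment.

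In the crossover the visit does carry one. Protocol 5.1 says that "during Week 7 subjects will cross-over to receive the other study treatment per the randomization schedule", so Visit 6 stands for the first treatment and Visit 7 for the second.

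Protocol 5.3.6 is broad: "If the subject is discontinued early (prior to Day 49), the following procedures will be performed". The list includes ADHD-RS-IV, CGI-I, C-SSRS, vital signs, weight, ECG and laboratory tests. It sets no limit on time since the last patch.

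The mapped values then reach tests as well as tables. SAP 7.1.3.3 states: "The ADHD-RS-IV Total and subscale scores at Visits 6 and 7 will be analyzed in a similar way to the primary efficacy analysis". SAP 7.1.3.5 compares dichotomised CGI-I at the same visits by the McNemar, Mainland-Gart and Prescott tests. Both sections name the FAS, which "includes all consented and randomized subjects who have taken at least one dose of study medication". SAP 7.7.3 notes that laboratory data exist only at screening and at Visit 7 or ET, and summarises them by treatment arm. For a child who leaves because of side effects or worsening symptoms, Protocol 5.3.7 says that "usual ADHD treatment may be resumed at the discretion of the investigator".

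**The concern.** A rule that is harmless in the open-label phase changes meaning once the visit label is also the treatment label. Moving a value forward across the Visit 6 to Visit 7 boundary, or from Visit 5 to Visit 6, can move it to another treatment. No text ties an ET value to the treatment last worn, limits the time since the last patch, or excludes values taken on another ADHD drug.

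At stake are the d-ATS versus placebo contrasts for ADHD-RS-IV and CGI-I, and the treatment columns for laboratory tests, vital signs, ECG and C-SSRS. The distortion need not be neutral. A placebo-first child who leaves straight after Visit 6 because symptoms worsened would add a poor score to the d-ATS column.

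**Working it through.** **Step 1. Follow the rule for each withdrawal time after randomisation.**

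| Child stops | ET ADHD-RS-IV, CGI-I, vital signs, ECG, C-SSRS stored as | ET laboratory values stored as | Correct treatment? |
|---|---|---|---|
| After Visit 5, before the Day 36 patch | Visit 6 | Visit 7 | No double-blind patch worn; the last treatment was open-label d-ATS |
| During Week 6, wearing that week's patches | Visit 6 | Visit 7 | Yes, except laboratory values |
| After Visit 6, before the first Week 7 patch | Visit 7 | Visit 7 | No; second treatment never worn |
| During Week 7, wearing that week's patches | Visit 7 | Visit 7 | Yes |

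In the double-blind phase weight is scheduled on Day 49 only (Protocol 5.3.5.3), so it follows the laboratory column if it is tabulated.

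**Step 2. Effect on each analysis.**
- *Row 3* gives a child with a genuine Visit 6 value a false Visit 7 value, and hence a false pair. For CGI-I, a false pair with the same response twice is concordant: it does not count in McNemar or Mainland-Gart but enters Prescott, which includes children with no preference. If the response changed between Visit 6 and ET, the pair counts in all three tests.
- *Row 1* matters only if the child is in the FAS. The definition does not say whether open-label doses qualify. If they do, a placebo-first child contributes a d-ATS value as placebo to the summaries and the ADHD-RS-IV model. There is no Visit 7 ADHD-RS-IV or CGI-I value, so no pair is formed and the paired CGI-I tests are untouched.
- *Resumed ADHD treatment* can affect any row. Protocol 5.3.7 allows resumption at withdrawal, 5.3.6 sets no ET window, and neither fixes the order of the two.
- *Not affected:* SKAMP, PERMP and CPRS-R:S are not ET procedures. Adverse events are assigned by start date, with follow-up events going to the last treatment received (SAP section 5 and 7.7.1).

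**Step 3. How many children.** The plan gives no count of such withdrawals. Expected non-completers: 90 − 74 = 16 (17.8% of 90), or 20% × 90 = 18 from the stated dropout rate. This is a ceiling on all double-blind withdrawals, not an estimate of row 3.

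**Step 4. Size for ADHD-RS-IV, as an illustration.** Assume 74 true pairs with mean difference D, and m false pairs whose Visit 7 value still reflects the first treatment (difference 0).

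Estimate = D × 74/(74 + m); attenuation = m/(74 + m).
- m = 2: 2/76 = 2.6%
- m = 4: 4/78 = 5.1%
- m = 8: 8/82 = 9.8%
- m = 16 (the ceiling): 16/90 = 17.8%

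The same factor follows from period-by-treatment cell means, with m split evenly between sequences. Period 1 is unaffected and gives D. In period 2 each cell holds a share m/(74 + m) of wrong-treatment values, giving D × (1 − 2m/(74 + m)). The average of the two is D × (1 − m/(74 + m)).

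**The case against.** The best defence has four parts. First, the mapping applies only where appropriate, and SAP section 7 says table headers count children who received the treatment; together these suggest that a sensible programmer would not place a child under a treatment never worn. Second, the window is narrow: Visit 6 runs to 12 hours after dosing on Day 42, and the next patch is due the following morning. Third, ADHD-RS-IV and CGI-I lie outside the closed testing family, safety has no inferential tests, and the Completers set requires both classroom sessions, so it contains no double-blind ET values. Fourth, SAP 6.3 has an as-treated rule.

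The second and third parts stand as limits on size. The first does not remove the problem. No criterion is written, and a mapped child would be counted in the body of a table but not in its header. The as-treated rule covers only the Safety population and errors in arm assignment. SAP 7.1.3.3 and 7.1.3.5 specify the FAS, not Completers.

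A reader might infer more than the documents support:
- *That all 16 non-completers are misassigned.* Withdrawals during a week of patch wear map correctly for ADHD-RS-IV and CGI-I.
- *That a child who stops before Day 36 reverses the sign of a within-child difference.* That child has no pair, and FAS membership is itself unclear.
- *That ET scores will be taken on resumed medication.* The text permits this but does not show it. Protocol 7.4.3 bars other stimulants during the study, and the provision for scheduling an ET visit later (Protocol 5.3.4.2) concerns children who do not reach an optimal dose.
- *That resumed medication would reverse the effect.* Full reversal of a d-ATS-first child's difference would need usual treatment to beat d-ATS by the whole of D, and nothing in the documents supports that.

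**Conclusion.** The concern holds for a defined set of cases. Followed as written, SAP section 7 assigns secondary efficacy and non-AE safety values to a treatment never worn when a child stops between Visit 6 and the first Week 7 patch, and does so for laboratory values from any Week 6 withdrawal. Two further routes are open but conditional: withdrawal between Visit 5 and Day 36, which depends on how the FAS is read, and ET scores after usual ADHD treatment is resumed.

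The primary SKAMP result and adverse events are not affected. The likely effect on ADHD-RS-IV is small: about 2.6% attenuation for two false pairs and 5.1% for four. These figures assume 74 true pairs and false pairs with zero difference; the documents do not give m. If the ET visit falls well after the last patch, or after other medication, the zero-difference assumption fails and the bias may go either way. The rule should be changed because it is wrong on its face for the crossover and cheap to correct, not because a large bias has been shown.

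**What to change.** In SAP section 7, add a rule for the double-blind phase.

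- **ADHD-RS-IV and CGI-I.** Use an ET value as Visit 6 or Visit 7 only if at least one patch of that period was applied, the assessment falls within a stated interval of the last patch of that period, and no other ADHD medication was started before it. Otherwise treat the visit as missing and list the value under ET.
- **Laboratory tests, vital signs, ECG, weight and C-SSRS.** Keep the ET value in the tables under the treatment last applied, as SAP 7.7.1 already does for follow-up adverse events. Flag it if other ADHD medication was started first. Where the child already has a scheduled value under that treatment, show the ET value in a separate row. Moving these values to listings only would remove early leavers' sole post-baseline laboratory results from the tables.
- **FAS.** State whether the qualifying dose must be a double-blind dose.

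The cost is SAP wording and a programming rule. Dosing diaries, concomitant medication records and visit dates are already collected, and SAP section 1 provides for a final SAP version before database lock, so the rule can be set blind. The downside is that a few ET values leave the ADHD-RS-IV and CGI-I analyses.
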